**PROTOCOL HISTORY**

Version	Date
Amended Protocol CTP v7.0	11 APR 2024
Amended Protocol CTP v6.0	18 AUG 2023
Amended Protocol CTP v5.0	02 MAY 2023
Amended Protocol CTP v4.0	24 AUG 2022
Amended Protocol CTP v3.0	16 MAR 2022
Amended Protocol CTP v2.0-CZ1 (Czech Republic Local Amendment 1 of CTP v2.0)	19 JAN 2022
Amended Protocol CTP v2.0	18 OCT 2021
Original Protocol CTP v1.0	10 AUG 2021

**LIST OF FIGURES**

# 1 PROTOCOL SYNOPSIS

## Protocol title

A Phase 1b/2, Open-Label, Multicenter Study to Evaluate the Safety and Pharmacokinetics of a Modified Tafasitamab IV Dosing Regimen Combined With Lenalidomide (LEN) in Patients With Relapsed or Refractory Diffuse Large B-Cell Lymphoma (R/R DLBCL) [MINDway]

## Objectives, endpoints and estimands

The following objectives and endpoints will be evaluated in the study, see [Table 1](#):

**Table 1: Objectives and Corresponding Endpoints**

Objectives	Endpoints
Primary	

 
To evaluate the safety and tolerability of tafasitamab administered ██████████ in combination with lenalidomide in R/R DLBCL patients
 
To determine a recommended dose for tafasitamab ██████████ administration in combination with lenalidomide in R/R DLBCL patients
 
	Incidence and severity of TEAEs
Secondary	
To evaluate the pharmacokinetic profile of tafasitamab after ██████████ dosing in combination with lenalidomide	Tafasitamab serum concentrations after 3 ( $C_{trough}$ and $C_{max}$ ) and 12 ( $C_{trough}$ ) treatment cycles
To assess anti-tumor activity of tafasitamab after ██████████ dosing in combination with lenalidomide	
 
Best Objective Response Rate (ORR) by investigator assessment up to treatment Cycle 12 based on Cheson et al. (2007)
 
Duration of Response (DoR) by investigator assessment based on Cheson et al. (2007)
 
Progression-Free Survival by investigator assessment based on Cheson et al. (2007)
 

To assess the incidence of anti-drug antibodies to tafasitamab	Number and percentage of patients developing anti-tafasitamab antibodies up to treatment Cycle 12

Abbreviations:  $C_{max}$ =maximum concentration;  $C_{trough}$ =minimum concentration; DLBCL=diffuse large B-cell lymphoma; ██████████; R/R=relapsed/refractory; TEAEs=treatment-emergent adverse events. Each treatment cycle is 28 days.

## Estimands

The primary clinical question of interest is: Given a proposed ██████████ treatment ██████████ with tafasitamab ██████████, what is the observed incidence and severity of treatment emergent adverse events (TEAEs) in R/R DLBCL patients who receive ██████████? This would allow the assessment of the safety and the tolerability of ██████████. The primary estimand and its attributes are described in [Section 4](#). Possible intercurrent events and strategies to capture them are described in [Section 4](#).

## Study design

MOR208C115 (MINDway) is an open-label, multicenter, phase 1b/2 study of tafasitamab combined with lenalidomide (LEN) to evaluate the safety and pharmacokinetics (PK) of a [REDACTED] tafasitamab [REDACTED] in adult patients with R/R DLBCL.

Overall, approximately 51 patients will be enrolled in the study. Patients will receive LEN in combination with tafasitamab in 28-day cycles. The [REDACTED] tafasitamab [REDACTED] will be investigated in a stepwise design with two sequential cohorts followed by an expansion cohort at the recommended dose level. Tafasitamab will be administered as intravenous infusion [REDACTED] [REDACTED] (see [Table 2](#)).

[REDACTED]

LEN (25 mg) will be administered for a maximum of 12 cycles or until disease progression, unacceptable toxicity, withdrawal, death or lost to follow up, whichever comes first. After Cycle 12 or LEN discontinuation, patients will continue with tafasitamab monotherapy [REDACTED] [REDACTED] until disease progression, unacceptable toxicity, withdrawal, death or lost to follow up, whichever comes first.

No follow-up for overall survival will be performed in this study after end of treatment (EOT).

A Data and Safety Monitoring Committee (DSMC), consisting of Sponsor representatives and investigators, will continuously monitor the study and can recommend to stop enrollment at any time based on emerging safety data. In addition, pre-defined DSMC meetings will take place when at least 6 patients have completed the 5-week (35 day) safety observation period in Cohort 1 and Cohort 2, respectively.

Details of specific responsibilities, composition, meeting formats and frequency of the DSMC are outlined in the DSMC Charter.

### **Study population**

The study will enroll approximately 51 patients with histologically confirmed diagnosis of R/R DLBCL (as specified in inclusion criterion 3) based on the local pathology report.

All patients must meet below listed eligibility criteria to be enrolled in the study. Prospective approvals of deviations to eligibility criteria, also known as protocol waivers or exemptions, are not permitted.

### **Inclusion criteria**

Patients are eligible to be included in the study only if all the following criteria apply:

1. Capable of giving signed informed consent as described in [Appendix 2: Regulatory, Ethical, and Trial Oversight Considerations](#), which includes compliance with the requirements and restrictions listed in the informed consent form (ICF) and in this protocol.
2. Patient must be at least 18 years of age and of legal age (whichever is higher) in the jurisdiction in which the study is taking place at the time of signing the informed consent.
3. One of the following histologically confirmed diagnoses:
  - DLBCL not otherwise specified (NOS)
  - T cell/histiocyte-rich large B-cell lymphoma (THRLBCL)
  - Epstein-Barr virus (EBV) positive DLBCL of the elderly (EBV-positive DLBCL)
  - Grade 3b Follicular Lymphoma
  - Composite lymphoma with a DLBCL component with a subsequent DLBCL relapse, according to the Revised European American Lymphoma/World Health Organization (REAL/WHO) classification.

Additionally, patients with the evidence of histological transformation to DLBCL from an earlier diagnosis of low-grade lymphoma (i.e., an indolent pathology such as follicular lymphoma, marginal zone lymphoma, chronic lymphocytic leukemia) into DLBCL with a subsequent DLBCL relapse are also eligible.

4. Tumor tissue for retrospective central pathology review must be provided as an adjunct to participation in this study. If archival formalin fixed paraffin embedded tumor tissue acquired  $\leq 3$  years prior to screening is not available, a fresh tumor tissue sample from the patient should be obtained. Archival formalin fixed- paraffin embedded tumor tissue acquired  $>3$  years prior to screening is acceptable only in cases where a fresh tumor biopsy cannot be collected due to a safety risk, e.g., due to co-morbidity, or inaccessible tumor site.

5. Patients must have:
  - a. Relapsed and/or refractory disease as defined in [Appendix 3: Study Specific Definitions](#)
  - b. At least one bi-dimensionally measurable disease site. The lesion must have a greatest transverse diameter of  $\geq 1.5$  cm and greatest perpendicular diameter of  $\geq 1.0$  cm at baseline. The lesion must be positive on positron emission tomography (PET) scan (for definition see [Juweid \*et al.\*, 2007](#))
  - c. Received at least one, but no more than three previous systemic regimens for the treatment of DLBCL and one therapy line must have included a cluster of differentiation-20 (CD20) targeted therapy (e.g., rituximab [RTX])
  - d. An Eastern Cooperative Oncology Group (ECOG) performance status of 0 to 2.
6. Patients that are not eligible to undergo intensive salvage therapy including autologous stem cell transplantation (ASCT). The reason for a patient's ineligibility must meet one of the criteria described below and documented in the patient's source data:
  - a. Inadequate performance status (Karnofsky performance status  $\leq 80\%$ ; see [Appendix 5: Karnofsky Performance Status Scale](#))
  - b. Disease not responsive to salvage chemotherapy. Responsiveness is defined as a tumor demonstrating either complete response (CR) or partial response (PR) to salvage chemotherapy
  - c. Inadequate major organ function (any of the below):
    - i. symptomatic congestive heart failure
    - ii. lung function-forced vital capacity (FVC), forced expiratory volume in 1 second (FEV-1), and corrected diffusion capacity of the lung for carbon monoxide (DLCO)  $\leq 60\%$
    - iii. liver function-total serum bilirubin and transaminases  $> 2$  x upper limit of normal (ULN)
  - d. History or evidence of significant co-morbid medical or psychiatric illness which would significantly compromise the patient's clinical care and chances of survival
  - e. Inability to collect adequate stem cell graft (e.g.  $< 1-2 \times 10^6$  CD34+ cells free of tumor contamination/kg recipient body weight)
7. Patients must meet the following laboratory criteria at screening:
  - a. Absolute neutrophil count (ANC)  $\geq 1.5 \times 10^9/L$  (unless secondary to bone marrow involvement by DLBCL as demonstrated by recent bone marrow aspiration and bone marrow biopsy)
  - b. Platelet count  $\geq 75 \times 10^9/L$  (unless secondary to bone marrow involvement by DLBCL as demonstrated by recent bone marrow aspiration and bone marrow biopsy)
  - c. Total serum bilirubin  $\leq 2.5 \times ULN$  unless secondary to Gilbert's syndrome or documented liver involvement by lymphoma. Patients with Gilbert's syndrome or documented liver involvement by lymphoma may be included if their total bilirubin is  $\leq 5 \times ULN$  (see exclusion criterion 6g)

- d. Alanine transaminase (ALT), aspartate transaminase (AST) and alkaline phosphatase (ALP)  $\leq 3 \times \text{ULN}$  or  $< 5 \times \text{ULN}$  in cases of documented liver involvement
  - e. Serum creatinine CL must be  $\geq 60$  mL/minute either measured or calculated using a standard Cockcroft and Gault formula (see [Appendix 6: Cockcroft-Gault Formula](#))
8. Patients who received previous CD19 targeted therapy (other than tafasitamab) must have CD19 positive lymphoma confirmed on a biopsy taken since completing the prior CD19 targeted therapy
  9. Patients with primary refractory disease (see [Appendix 3: Study Specific Definitions](#)) who received at least one, but no more than three previous systemic regimens (including a CD20 targeted therapy) for the treatment of DLBCL are eligible.

### Exclusion criteria

Patients are excluded from the study if any of the following criteria apply:

1. General provisions:
  - a. Patients who are legally institutionalized, or patients under judicial protection
  - b. Concurrent enrollment in another interventional clinical study
2. Patients who have:
  - a. Any other histological type of lymphoma including primary mediastinal (thymic) large B-cell (PMBL) or Burkitt lymphoma
  - b. Known "double/triple hit" genetics (high grade B-cell lymphoma) characterized by simultaneous detection of *MYC* with *BCL2* and/or *BCL6* translocation(s) defined by fluorescence *in situ* hybridization. *MYC*, *BCL2*, *BCL6* testing prior to study enrollment is not required
3. Patients who have:
  - a. Not discontinued (within 14 days prior to Day 1 dosing): CD20 targeted therapy, chemotherapy, radiotherapy, investigational anticancer therapy or other lymphoma-specific therapy
  - b. Undergone major surgery (within 4 weeks prior to Day 1 dosing) or suffered from significant traumatic injury
  - c. Received live vaccines (within 4 weeks prior to Day 1 dosing) (see [Appendix 7: COVID-19: Infection Prophylaxis and Vaccines](#))
  - d. Required parenteral antimicrobial therapy for active, intercurrent infections (within 14 days prior to Day 1 dosing)
4. Patients who:
  - a. Have, in the opinion of the investigator, not recovered sufficiently from the adverse toxic effects of prior therapies
  - b. Were previously treated with tafasitamab or IMiDs® (e.g., thalidomide, LEN)
  - c. Have a history of hypersensitivity to compounds of similar biological or chemical composition to tafasitamab, IMiDs® and/or the excipients contained in the study treatment formulations

- d. Have undergone ASCT within the period  $\leq 3$  months prior to signing the ICF. Patients who have a more distant history of ASCT must exhibit full hematological recovery before enrollment into the study
  - e. Have undergone previous allogenic stem cell transplantation
  - f. Have a history of deep venous thrombosis/embolism, threatening thromboembolism or known thrombophilia or are at high risk for a thromboembolic event in the opinion of the investigator and who are not willing/able to take venous thromboembolism (VTE) prophylaxis during the entire treatment period
  - g. Concurrently use other anticancer or experimental treatments
5. History of other malignancy that could affect compliance with the protocol or interpretation of results. Exceptions:
- a. Patients with any malignancy appropriately treated with curative intent and the malignancy has been in remission without treatment for  $> 2$  years prior to enrollment are eligible
  - b. Patients with low-grade, early-stage prostate cancer (Gleason score 6 or below, Stage 1 or 2) with no requirement for therapy at any time prior to study are eligible
6. Patients with:
- a. Positive hepatitis B and/or C serology (see [Appendix 8: Hepatitis Virus Serology](#) for details)
  - b. Known seropositivity for or history of active viral infection with human immunodeficiency virus (HIV)
  - c. Central nervous system (CNS) lymphoma involvement – present or past medical history
  - d. History or evidence of clinically significant cardiovascular, CNS and/or other systemic disease that would in the investigator's opinion preclude participation in the study or compromise the patient's ability to give informed consent
  - e. History or evidence of rare hereditary problems of galactose intolerance, the Lapp lactase deficiency or glucose-galactose malabsorption
  - f. Gastrointestinal (GI) abnormalities (issue with absorption) including the inability to take oral medication
  - g. History or evidence of severe hepatic impairment (total serum bilirubin  $> 3$  mg/dL), jaundice unless secondary to Gilbert's syndrome or documented liver involvement by lymphoma (see inclusion criterion 7c)
  - h. History of hypersensitivity to any of the study treatments or its excipients or to drugs of similar chemical class
  - i. Any other medical condition which, in the investigator's opinion, makes the patient unsuitable for the study

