## 2 SCHEDULE OF ASSESSMENTS (SoA)

**Table 3: Schedule of Assessments**

Evaluation or Procedure	Screening Period	Treatment Period (Cycle = 28 days)												Follow-Up Period
	Screening ≤28 Days prior to D1	Cycle 1			Cycle 2		Cycle 3		Cycle 4-12	Cycle 12	Cycle 13 onwards	End of Treatment Visit (EOT) 	90-Day Safety Follow-up Visit/ End of Study Visit 	
Day	Screen	D1	D4 ±1 day	D8 ±1 day	D15 ±1 day	D1 ±1 day	D15 ±1 day	D1 ±1 day	D15 ±1 day	D1 ±2 days	D28 ±2 days	D1 ±2 days	Within 14 days after decision on treatment discontinuation	±7 days
Starting Evaluations and Eligibility														
Informed consent	X													
Inclusion/exclusion criteria	X	X 												
Demography	X													
Medical history/current medical condition	X													
Disease history/staging/Ann Arbor	X													
Disease risk assessment (IPI)	X													
Throughout Evaluations														
Prior/concomitant therapy 	X	X	X	X	X	X	X	X	X	X		X	X	X
Physical examination (F – full, L – limited)	F	L						L		L 		L 	F	
ECOG performance status	X	X 				X		X		X			X	
Body weight/height 		X	X	X	X	X	X	X	X	X		X	X	
B-symptoms	X	X				X		X		X		X	X	
Vital signs 	X	X	X	X	X	X	X	X	X	X		X	X	
12-lead resting ECG	X	X 			X 	X 		X 		X 5a			X	
Adverse events (AEs, SAEs and AESIs)	X	X	X	X	X	X	X	X	X	X		X	X	X
Laboratory														
Urinalysis (local lab)	X	X				X		X		X			X	
Pregnancy test (FCBP) 	X	X 		X 	X 	X 		X 		X 		X 	X	
Pregnancy and risks counselling	X	X				X		X		X			X	
US only: pregnancy and risk interview	X	X				X		X		X			X	
Hematology and Serum chemistry (local lab) 	X	X	X	X	X	X	X	X	X	X		X	X	
Serology Hepatitis B (local lab)	X													

Evaluation or Procedure	Screening Period	Treatment Period (Cycle = 28 days)												Follow-Up Period
	Screening ≤28 Days prior to D1	Cycle 1				Cycle 2		Cycle 3		Cycle 4-12	Cycle 12	Cycle 13 onwards	End of Treatment Visit (EOT) 	90-Day Safety Follow-up Visit/ End of Study Visit 
Day	Screen	D1	D4 ±1 day	D8 ±1 day	D15 ±1 day	D1 ±1 day	D15 ±1 day	D1 ±1 day	D15 ±1 day	D1 ±2 days	D28 ±2 days	D1 ±2 days	Within 14 days after decision on treatment discontinuation	±7 days

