## 5 STUDY DESIGN

### 5.1 Overall Design

MOR208C115 (MINDway) is an open-label, multi-center, phase 1b/2 study of tafasitamab combined with LEN to evaluate the safety and PK [REDACTED] in adult patients with R/R DLBCL.

Patients will receive LEN in combination with tafasitamab in 28-day cycles. [REDACTED]

Tafasitamab will be administered as intravenous infusion according to the following dosing schedule:

- [REDACTED]
- [REDACTED]
- [REDACTED]
- [REDACTED]

LEN (25 mg) will be administered for a maximum of 12 cycles or until disease progression, unacceptable toxicity, withdrawal, death or lost to follow up, whichever comes first. After cycle 12 or LEN discontinuation, patients will continue with tafasitamab monotherapy [REDACTED] until disease progression, unacceptable toxicity, withdrawal, death or lost to follow up, whichever comes first.

[REDACTED]

[REDACTED]. If a patient discontinues the study for reasons other than safety before the completion of the predefined safety observation window (5 weeks) as per [Section 8.4](#), the patient may be replaced.

[REDACTED]

A patient is considered to have started the study and entered the screening period when they have signed the informed consent form.

[REDACTED]  
[REDACTED]  
[REDACTED]. This safety window will also be maintained [REDACTED]  
[REDACTED]

Patient is considered enrolled in the study if they received at least one dose of any study treatment (tafasitamab or LEN).

The end of the study is reached for an individual patient if any of the following applies: withdrawal, lost to follow up, death or completion of the end of study (EOS)/90-Day Safety Follow-up visit after treatment discontinuation. Regardless of the reason for treatment discontinuation on study (with the exception of withdrawal of consent, death or lost to follow up) all patients must complete a Safety Follow-up visit 90 days after the last dose of study treatment, see [Section 2](#).

The end of the study is reached when all patients still on study treatment have been followed for at least 3 years, or when the final patient on study has completed their last visit, whichever comes first.

Patients who are receiving ongoing treatment at the end of study may continue treatment with either of the options below upon assessment of a clinical benefit of continued treatment by the investigator and in accordance with the local regulatory guidance:

- commercially available tafasitamab for the approved dose regimen locally; or

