### 7.8.3 Anticancer Therapies

Patients should not have received a CD20 targeted therapy, chemotherapy, radiotherapy, investigational anticancer therapy or other lymphoma specific- therapy within 14 days prior to Cycle 1 day 1 of the study. In addition, no radiotherapy (including limited field radiotherapy) is permitted after the baseline PET/computed tomography (CT) scan for initial disease assessment has been performed. Other than the study drugs, patients should not receive any other DLBCL specific- therapy during the study treatment period. The patient should not receive any investigational agent other than tafasitamab and LEN during the treatment period of the study.

After disease progression has been recorded, additional antineoplastic therapies are permitted at the discretion of the investigator and in accordance with the local guidelines and should be recorded in the eCRF.

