#### ***7.8.4.1 Screening***

Patients may potentially receive systemic glucocorticosteroids in doses above 20 mg/day (prednisone or equivalent) to manage severe DLBCL manifestations (e.g., compressive disease, rapidly progressing symptomatic adenopathy) during Screening as per institutional standards. For these patients the glucocorticosteroids treatment needs to be tapered to a total daily dosage of 20 mg or less of prednisone or its equivalent prior to study treatment(s) administration on Cycle 1, Day 1.

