## 7.9 Prohibited Medication/Therapy

No radiotherapy is permitted after the screening PET/CT scan for initial disease assessment has been performed.

The use of concurrent antineoplastic therapies other than study drugs, including, but not limited to, chemotherapies, hormonal therapy, immunotherapy, biological response modifiers, mAbs with or without conjugation, radioisotopic therapies, stem cell transplant and targeted small molecules are not permitted during the entire treatment period of this study.

The patient may not receive any investigational agent other than tafasitamab and LEN during the treatment period of the study.

After disease progression/relapse has been observed, additional anti-lymphoma therapies are permitted at the discretion of the investigator and in accordance with the local treatment guidelines. These therapies should be recorded in the eCRF as next anti-lymphoma treatments.

Live vaccines must not be administered to patients during the treatment and up-to 90 days after the last dose of the study drug in this study. Killed, inactivated vaccines, such as an injectable annual influenza vaccine, are permitted. Investigators should follow institutional guidelines concerning infection chemoprophylaxis for patients regarded to be at high risk for infection. See [Appendix 7: COVID-19: Infection Prophylaxis and Vaccines](#).

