### 9.3.1 Radiographic Imaging Assessment

*Initial disease and disease response assessments* will be made by positron emission tomography PET CT (CT should be done with IV contrast) or PET-MRI at the time points indicated in the SoA (see [Section 2](#)). Additional radiographic assessments may be performed by the investigator during the course of the study, if deemed necessary.

If progression/relapse is suspected on the basis of clinical symptoms, PET-CT or PET-MRI should be performed to confirm disease progression.

*Tumor measurements and disease assessment* (local) will be performed as indicated in [Section 2](#) by CT. The CT portion of PET/CT will be acceptable in place of CT for tumor measurement and disease assessment, *only* when the CT portion is of adequate diagnostic-quality, and using adequate intravenous contrast.

Magnetic resonance imaging (MRI) may be used in lieu of CT, and PET-MRI in lieu of PET-CT for patients with contraindications to the administration of contrast agents, or due to other medical reasons, at the same time points as CT, or in addition to CT, at the discretion of the investigator (in this case, MRI may be performed as/when appropriate). The method used at baseline should be used throughout the study unless otherwise medically indicated.

If available and of acceptable quality, previously performed PET-CT or PET-MRI examinations, in accordance with the standard of care, that were done up to four weeks prior to the date of informed consent may be used for a patient's baseline radiology assessment. Additional PET-CT

or PET-MRI or CT or MRI examinations may be performed by the investigator in the course of the study, if deemed necessary (e.g., to confirm the occurrence of a CR or to make important treatment-related decisions). Whenever feasible, in such cases the investigator should seek prior approval of the sponsor for the additional imaging.

If the patient discontinues from treatment, a PET-CT or PET -MRI scan is only required at the EOT Visit if it was not performed in the cycle prior to the end of treatment or if disease progression was not already radiologically confirmed. CT may be performed in lieu of PET-CT if the patient discontinues from treatment within Cycle 1

The same scan modality should be used for all assessments, and all patients are required to have scans of the neck/chest/abdomen/pelvis.

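### The baseline PET may predate the last lymphoma therapy or DLBCL-directed steroids, so tumour shrinkage before Day 1 can be scored as response or mask early progression

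*Protocol*

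**What the plan says.** **Protocol**
- Exclusion criterion 3a (Synopsis and Section 6.2) covers patients who have "Not discontinued (within 14 days prior to Day 1 dosing): CD20 targeted therapy, chemotherapy, radiotherapy, investigational anticancer therapy or other lymphoma-specific therapy". Section 7.8.3 repeats the 14-day limit.
- Table 3 heads the screening column "Screening ≤28 Days prior to D1", and Section 5.1 starts that period at consent: "A patient is considered to have started the study and entered the screening period when they have signed the informed consent form".
- Section 9.3.1 allows standard-of-care PET-CT or PET-MRI examinations "that were done up to four weeks prior to the date of informed consent may be used for a patient's baseline radiology assessment". It sets no condition on treatment given after such a scan.
- On therapy after the scan, Section 7.8.3 says "no radiotherapy (including limited field radiotherapy) is permitted after the baseline PET/computed tomography (CT) scan", and Section 7.9 says "No radiotherapy is permitted after the screening PET/CT scan for initial disease assessment has been performed". Neither extends this to systemic therapy.
- Section 7.8.4.1 on Screening: "Patients may potentially receive systemic glucocorticosteroids in doses above 20 mg/day (prednisone or equivalent) to manage severe DLBCL manifestations". The condition is a taper to 20 mg/day or less before the first dose. Section 7.8.4 discourages systemic steroids because their own activity against lymphoma could confound the reading of study-treatment effect.
- Section 9.3.2 accepts a bone marrow result from before consent only where the disease has been stable since. Section 9.3.1 has no matching condition for the PET.

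**SAP**
- Section 4.1.4 takes the last non-missing value before first dose as baseline and gives no maximum age.
- Section 7.3.1 disregards responses documented after non-study antilymphoma treatment begins, but Section 6.5.5 counts such treatment only from the start of study drug.

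**The concern.** A PR under Appendix 4 is a fall of at least 50% in the summed lesion products, and a CR in PET-positive disease requires the lesion to become PET-negative. Both presuppose a baseline that describes the disease when study drug starts. If therapy or steroids are given between the scan and Day 1, the disease may already be smaller or less active at Day 1 than the baseline records, and that difference is credited to tafasitamab plus lenalidomide.

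The protocol recognises this for radiotherapy, which it bars after the scan, and names steroids as a confounder. It does not carry the same reasoning over to systemic therapy or to steroids given in Screening. At stake is an upward bias in ORR, and in progression at the first on-study scan. A confidence interval does not reflect a bias of this kind.

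**Working it through.** The documents give no figure for the maximum age of the baseline scan, so there is none to reproduce. As a check on method, the exact Clopper-Pearson interval for 46/80 is 45.9% to 68.5%, which matches Protocol Table 6 for the earlier pivotal trial. The same method is used in step 4.

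**1. Oldest permitted baseline scan.** Four weeks before consent (9.3.1) plus up to 28 days of screening (Table 3): 28 + 28 = 56 days before Day 1.

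**2. Time open to treatment after the scan.**
- Systemic therapy, oldest scan: 56 − 14 = 42 days.
- Systemic therapy, scan on the first day of screening: 28 − 14 = 14 days.
- DLBCL-directed steroids above 20 mg/day: anywhere in Screening, so up to 28 days, subject to the taper. This holds even with a scan done inside the screening period, so it does not depend on the 56-day worst case.

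**3. Share of the first assessment interval that precedes study drug.** C3D1 is study day 2 × 28 + 1 = 57, which is 56 days after Day 1. The first CT falls within 4 days before it (Table 3, footnote 11a). The interval from the oldest permitted baseline to that CT is therefore 56 + 56 = 112 days, or 108 if the CT is 4 days early. The pre-treatment share is at most 56/112 = 50% to 56/108 = 52%.

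**4. Effect on ORR.** With about 51 patients, each misattributed responder adds 1/51 = 1.96 percentage points. As illustration only, 29/51 is 56.9% (95% CI 42.2 to 70.7); with two misattributed responders, 31/51 is 60.8% (46.1 to 74.2), a shift of 3.9 points.

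**5. Which endpoints are reached.**
- *ORR:* directly, through CR or PR.
- *PFS:* directly only at the first on-study scan, where baseline is the reference for growth. From then on Appendix 4 measures progression from nadir.
- *DoR:* indirectly. It starts at first documented response (SAP 7.3.3) and ends at nadir-based progression or death. A misattributed responder enters the DoR set, but the clock does not run from baseline.

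**6. Which patients are reached.** Under Appendix 3, relapse means new or growing disease after the most recent systemic therapy, and disease refractory to last treatment means less than a PR to it. A regimen given after the scan should therefore itself have failed. Two openings remain. Primary refractory disease is judged on first-line therapy alone, and inclusion criterion 9 admits such patients after up to three regimens. And therapy may continue after a scan that showed less than a PR, since nothing requires the baseline scan to follow the last dose. Appendix 3 does not address steroids.

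**The case against.** The strongest case against is that eligibility and the SAP already deal with most of this.

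- *Appendix 3 requires failure of the last therapy.* This largely stands for chemotherapy and anti-CD20 therapy, apart from the two openings above. If failure was shown on a later scan, SAP 4.1.4 would point to that scan as baseline. But a later scan is not required, and the analysed response is the one the investigator records (SAP 7.1).
- *The per-protocol analyses could remove affected participants.* They are planned for ORR, PFS and DoR, and SAP Table 2 allows exclusion for conditions that influence efficacy. That wording is general. Treatment that complies with the protocol is not a deviation, and this case is not named.
- *Exclusion 4g bars concurrent anticancer treatment.* It does not reach therapy that ended 15 to 56 days before Day 1.
- *The endpoints are secondary and descriptive.* This stands. The primary endpoint is the incidence and severity of TEAEs, which this route does not touch, and no formal test is planned.

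A reader might also infer more than the documents support. One tempting reading is that ORR, DoR and PFS are all measured from the baseline scan, so that all are inflated and progression is generally delayed. Appendix 4 and SAP 7.3.3 contradict that: after the first scan progression is judged from nadir, and a lower nadir makes later progression easier to reach, not harder. Another is that a definite number of points of ORR is at risk. The documents give neither the frequency of treatment after the scan nor the chance of responding to it, so any such range would rest on invented inputs.

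**Conclusion.** The gap is real but narrow. In the worst case the baseline PET is 56 days old, with up to 42 days after it open to systemic lymphoma therapy. Steroids above 20 mg/day for DLBCL are permitted in Screening whatever the age of the scan, and this is the main route. For patients so treated, shrinkage before study drug can be counted as CR or PR, or can mask progression at the first on-study scan; later progression and DoR are affected only indirectly.

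The size per misattributed responder is about 2.0 points of ORR, assuming about 51 patients in the denominator. The total cannot be derived from the documents. The 56 days needs both windows at their maximum and is not a typical scan age. Priority is low to moderate.

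**What to change.** 1. **Protocol 9.3.1.** Accept an earlier standard-of-care PET as baseline only if it was done after the last dose of any systemic lymphoma-directed therapy. Otherwise use the screening PET already listed in Table 3.
2. **SAP Section 7.3.** Flag participants whose last lymphoma-directed therapy, or any DLBCL-directed steroid above 20 mg/day, falls between the baseline scan and Day 1. Report their number, and add a sensitivity analysis of ORR, PFS and DoR without them. This also covers participants already enrolled and the up to 14 days that can remain open when the PET is done early in screening.

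No steroid or washout rule needs to change, and a repeat PET for steroid-treated patients should not be required. Steroids are best handled through the sensitivity analysis.

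The data largely exist: therapy start and end dates are listed (SAP 6.5.3), and medication records carry dose, indication and dates (Protocol 7.8). One limit is that Section 7.8 specifies symptom-control steroids only for the three weeks before consent. With the oldest permitted scan, 28 − 21 = 7 days may go unrecorded.

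Cost: one sentence in the protocol and one extra table. A few patients could not reuse an earlier scan and would have the screening PET.
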